### **Prior/Concurrent Clinical Study Experience**

15. Participation in the study would result in loss of blood or blood products in excess of 500 mL within 56 days.
16. Exposure to more than 4 new chemical entities within 12 months prior to the first dosing day.
17. Current enrolment or past participation within the last 30 days before signing of consent in any other clinical study involving an investigational study intervention or any other type of medical research.

### **Diagnostic assessments**

18. Positive human immunodeficiency virus (HIV) antibody test
19. Presence of Hepatitis B surface antigen (HBsAg) at screening or within 3 months prior to first dose of study intervention.
20. Positive Hepatitis C antibody test result at screening or within 3 months prior to first dose of study intervention.

**NOTE:** Participants with positive Hepatitis C antibody due to prior resolved disease can be enrolled, only if a confirmatory negative Hepatitis C RNA test is obtained.

21. Positive Hepatitis C RNA test result at screening or within 3 months prior to first dose of study intervention.

**NOTE:** Test is optional and participants with negative Hepatitis C antibody test are not required to also undergo Hepatitis C RNA testing.

22. Positive pre-study drug/alcohol screen
23. Any history of substance abuse or a positive test for drugs of abuse at screening or admission
24. A positive highly sensitive pregnancy test (urine or serum as required by local regulations) at screening.
25. A positive laboratory confirmation of COVID-19 infection, or high clinical index of suspicion for COVID-19.

#### **Other Exclusions**

26. Part 1 (Food Effect): Participant must have no dietary restrictions (e.g., lactose intolerance) or inability to eat a high fat meal.
27. Regular alcohol consumption within 6 months prior to the study defined as:  
An average weekly intake of >21 units for males or >14 units for females. One unit is equivalent to approximately (250 ml) of beer, (100 ml) of wine or (35 ml) measure of spirits
28. Positive smoke breathalyzer indicative of smoking history at screening and each in-house admission to the clinical research unit or regular use of tobacco- or nicotine-containing products (e.g. nicotine patches or vaporizing devices) within 6 months prior to screening.
29. Hypersensitivity to any of the study interventions, or components thereof, or drug or other allergy that, in the opinion of the investigator or medical monitor, contraindicates participation in the study.

### **5.3. Lifestyle Considerations**

#### **5.3.1. Meals and Dietary Restrictions**

- Standardized meals will be provided while the participant is confined to the clinical unit. At all mealtimes, food will be served only after the completion of protocol specific procedures.
- Refrain from consumption of red wine, Seville oranges, grapefruit or grapefruit juice, pomelos, exotic citrus fruits, grapefruit hybrids, or fruit juices from 7 days before the first dose of the study until after the final dose.
- Water is allowed as desired except one hour before and two hours after dosing, except for the glass of water needed to administer the study intervention (e.g. maximum 240 mL).
- Meals will be provided at approximately 4 hours and 10 hours, respectively, after dosing. A light snack would be at approximately 13 hours post-dose and is finished prior to the overnight 8 hour fast, when fasting is applicable.
- Meals on Day-1 will follow the Day 1 schedule.

### 5.3.1.1. Fasted Conditions

- In Part 1 (except food effect), participants will fast from food and drink (except water) at least 8 hours prior to dose and no food is allowed until 4 hours post-dosing on Day 1 (Parts 1 and 2) and Day 7 (Part 2 only). Meals at all other times will be provided at times that should not interfere with fasting requirements for clinical laboratory testing. See the study reference manual (SRM) for additional details.

### 5.3.1.2. Fed Conditions

- For the Food Effect, participants will be fed a standard FDA high fat/high calorie meal after at least 8 hours of fasting and completion of pre-dose assessments (see [Table 8](#) for a description of the standard FDA high fat/high calorie meal.). The meal will be provided approximately 30 minutes prior to administration of study intervention. Study participants must consume the entire meal in 30 minutes or less. Noncompliance will be recorded as well as the amount of the meal not eaten.
- The high fat/high calorie meal provided in the Food Effect should derive approximately 150, 250, and 500-600 calories from protein, carbohydrate, and fat, respectively. The caloric breakdown of the test meal will be outlined in the study report. Substitutions in this test meal can be made if the meal provides a similar number of calories from protein, carbohydrate, and fat and has comparable meal volume and viscosity.

**Table 8 Standard FDA High Fat, High Calorie Diet**

Food	Quantity	Carbohydrate (g)	Protein (g)	Fat (g)	Calories
2 eggs fried in butter	2 eggs / 1 tsp butter	1.2	12.6	10 + 7.6	213
Bacon	2 strips	0	8	10	121
Hash brown potatoes	4 oz	20	3	2	125
Whole milk	8 oz	12	8	8	145
Toast	2 slices	30	5	2	180
Pats of butter	2 tsp	0	0	15.2	136
Total		58.2	36.6	53.8	920

These fasting requirements may be removed or modified at the discretion of the sponsor in consultation with the investigator

### 5.3.2. Caffeine, Alcohol, and Tobacco

- During each dosing session, participants must abstain from ingesting caffeine- or xanthine-containing products (e.g., coffee, tea, cola drinks, and chocolate) for 24 hours before the start of dosing until after collection of the final pharmacokinetic (PK) sample.
- During each dosing session, participants must abstain from alcohol for 24 hours before the start of dosing until after collection of the final PK sample.
- Use of tobacco products is not to be allowed from 6 months prior to screening until after the final follow-up visit.

### **5.3.3. Activity**

- Participants will abstain from strenuous exercise for 48 hours before each blood collection for clinical laboratory tests. Participants may participate in light recreational activities during studies (e.g., watching television, reading).
- Participants will remain in bed for 4 hours post-dosing on Day 1 (Parts 1 and 2) and Day 7 (Part 2 only).

### **5.4. Screen Failures**

Screen failures are defined as participants who consent to participate in the clinical study but are not subsequently randomized. A minimal set of screen failure information is required to ensure transparent reporting of screen failure participants to meet the Consolidated Standards of Reporting Trials (CONSORT) publishing requirements and to respond to queries from regulatory authorities. Minimal information includes demography, screen failure details, eligibility criteria, and any serious adverse events (SAEs).

Individuals who do not meet the criteria for participation in this study (screen failure) may be rescreened if the reason for screen failure is an ECG or lab value that, in the opinion of the investigator and/or Medical Monitor, is spurious or needs to be reconfirmed. Holter monitoring does not need to be repeated for the same participant being rescreened within three months of original screening. Rescreened participants should be assigned a new participant number.

Individuals who meet the eligibility criteria and are reserve participants who are subsequently not required for that cohort, could be used in other groups /later cohorts.

- If reserve participants are still within the screening window (30 days) no need to rescreen or assign a new subject number.
- If reserve participants are outside the screening window the site would reconsent the participant and complete the screening assessments (repeat bloods, ECG ,vitals etc).
- 24-hour Holter Monitor would still be valid if it is completed within 3 months of study start and need not be repeated.

### **5.5. Self-isolation**

Where it is site policy to do so, participants will be asked to attend the Unit a few days prior to admittance to receive a COVID-19 test. Once they have had this test they should be asked self-isolate at home until their admittance to the Unit for their next dosing period.

## 6. STUDY INTERVENTION

Study intervention is defined as any investigational intervention(s), marketed product(s), placebo, or medical device(s) intended to be administered to a study participant according to the study protocol.

### 6.1. Study Intervention(s) Administered

Study Intervention		
Product name:	GSK3882347	Placebo
Formulation description	Active Pharmaceutical Ingredient	Excipient
Dosage form	Capsule	Capsule
Unit dose strengths/Dosage levels	Active Pharmaceutical Ingredient (API) alone in capsule to be prepared by extemporaneous compounding to required weight. Multiple Capsules can be used as required. Fill weight can span from 11mg to 220mg as required (equates to 10 - 200mg dose)	To match active
Route of Administration	Oral	Oral
Dosing instructions	Study medication will be administered by the study personnel during each dosing day with approximately 240 mL of water	Study medication will be administered by the study personnel during each dosing day with approximately 240 mL of water
Physical description	Powder in capsule	Powder in capsule
Sourcing/Compounding	GSK, Addenbrookes Centre for Clinical Investigation (ACCI), CUC (Clinical Unit Cambridge), to provide blinded, labeled, API in capsule and Placebo capsules via Extemporaneous Compounding	GSK, ACCI, CUC (Clinical Unit Cambridge), to provide blinded, labeled, API in Capsule and Placebo capsules via Extemporaneous Compounding
Packaging and Labelling	Capsules provided in labelled HDPE bottles	Capsules provided in labelled HDPE bottles

### 6.2. Preparation/Handling/Storage/Accountability

Details on storage, handling, and allowable excursions for GSK3882347 investigational product (IP) and placebo will be provided in the Technical Terms of Supply (TTS).

1. A description of the detailed methods and materials required for preparation of GSK3882347 capsule and placebo are provided in the Technical Terms of Supply (TTS).
2. The capsules will be extemporaneously prepared at GSK, Addenbrookes Centre for Clinical Investigation (ACCI), CUC (Clinical Unit Cambridge) as per instructions in the Technical Terms of Supply (TTS) that will be reviewed and approved by GSK prior to use.
3. The investigator or designee must confirm appropriate temperature conditions have been maintained during transit for all study intervention received and any discrepancies are reported and resolved before use of the study intervention.
4. Only participants enrolled in the study may receive study intervention and only authorized site staff may supply or administer study intervention. All study interventions must be stored in a secure, environmentally controlled, and monitored (manual or automated) area in accordance with the labeled storage conditions with access limited to the investigator and authorized site staff.
5. The investigator, institution, or the head of the medical institution (where applicable) is responsible for study intervention accountability, reconciliation, and record maintenance (i.e., receipt, reconciliation, and final disposition records).
6. Further guidance and information for the final disposition of unused study intervention are provided in the Technical Agreement.
7. Under normal conditions of handling and administration, study intervention is not expected to pose significant safety risks to site staff.
8. A Safety Data Sheet /equivalent document describing occupational hazards and recommended handling precautions either will be provided to the investigator, where this is required by local laws, or is available upon request from GSK.

Precaution will be taken to avoid direct contact with the study intervention. A Safety Data Sheet describing occupational hazards and recommended handling precautions will be provided to the investigator. In the case of unintentional occupational exposure notify the monitor, Medical Monitor and/or GSK study contact.

### **6.3. Measures to Minimize Bias: Randomization and Blinding**

All participants will be randomized, according to the randomization schedule generated prior to the study by the Statistics Department at GSK. Each participant will be dispensed blinded study intervention, labeled with his/her unique randomization number, throughout the study. Each participant scheduled to receive study drug will receive a treatment allocation number when randomized. In Part 1(SAD), participants will be randomized in a 3:1 ratio and in Part 2 (MAD), participants will be randomized in a 4:1 ratio to receive study treatment (active drug: placebo). Part 1 will consist of two cohorts with up to a four-period for each cohort. Part 2 will consist of four cohorts for each of the MAD dose ([Figure 1](#)).

This will be a double-blind study with participants and the site staff blinded. The sponsor will be unblinded. For dose escalation, the Sponsor study team physicians, statistician, and clinical pharmacokinetic staff and/or their delegate will have access to unblinded data. Other Sponsor staff will remain blinded unless unblinding becomes necessary. The blind may be broken if, in the opinion of the investigator, it is in the participant's best interest for the investigator to know the study treatment assignment. The Sponsor study team must be notified before the blind is broken unless identification of the study treatment is required for a medical emergency in which the knowledge of the specific blinded study treatment will affect the immediate management of the participant's condition. In this case, the Sponsor study team must be notified within 24 hours after breaking the blind. The date and reason that the blind was broken must be recorded in the source documentation and CRF, as applicable.

Unblinded monitors, and in the event of a Quality Assurance audit, the auditor(s), will be allowed access to un-blinded study treatment records at the site to verify that randomization/dispensing has been done accurately.

A participant will be withdrawn if the participant's treatment code is unblinded by the investigator or treating physician. The primary reason for discontinuation (the event or condition which led to the unblinding) will be recorded in the CRF.

GSK's Global Clinical Safety and Pharmacovigilance (GCSP) staff may unblind the intervention assignment for any participant with an SAE. If the SAE requires that an expedited regulatory report be sent to one or more regulatory agencies, a copy of the report, identifying the participant's intervention assignment, may be sent to investigators in accordance with local regulations and/or GSK policy.

#### **6.4. Study Intervention Compliance**

- When the individual dose for a participant is prepared from a bulk supply, the preparation of the dose will be confirmed by a second member of the study site staff.
- When participants are dosed at the site, they will receive study intervention directly from the investigator or designee, under medical supervision. The date and time of each dose administered in the clinic will be recorded in the source documents. The dose of study intervention and study participant identification will be confirmed at the time of dosing by a member of the study site staff other than the person administering the study intervention. Study site personnel will examine each participant's mouth to ensure that the study intervention was ingested.

#### **6.5. Concomitant Therapy**

Any medication or vaccine (including over-the-counter or prescription medicines, vitamins, and/or herbal supplements) that the participant is receiving at the time of enrolment or receives during the study must be recorded along with:

- reason for use
- dates of administration including start and end dates

- dosage information including dose and frequency

The Medical Monitor should be contacted if there are any questions regarding concomitant or prior therapy.

#### **6.5.1. Permitted Medication and Non-Drug Therapies**

Paracetamol or Acetaminophen, at doses of  $\leq$  2 grams/day, is permitted for use any time during the study. Other concomitant medication may be considered on a case-by-case basis by the investigator in consultation with the Medical Monitor.

#### **6.5.2. Prohibited Medication and Non-Drug Therapies**

Participants must abstain from taking prescription or non-prescription drugs (including vitamins and dietary or herbal supplements) within 7 days (or 14 days if the drug is a potential enzyme inducer) or 5 half-lives (whichever is longer) before the first dose of the study until completion of the follow-up visit, unless, in the opinion of the investigator and Medical Monitor, the medication will not interfere with the study. This includes any medications which are substrates of CYP3A4 and sensitive to metabolic induction.

Use of a systemic antimicrobial within 30 days of screening.

#### **6.5.3. Rescue Medicine**

It is not anticipated that rescue medication will be required as this is a study in healthy participants.

### **6.6. Dose Modification**

The decision to proceed to the next dose level in both Part 1 (SAD) and Part 2 (MAD) will be made by the GSK study team and study investigator based on safety, tolerability, and preliminary PK data obtained from the prior dose level(s).

The dosing schedule may also be adjusted to expand a dosing cohort to further evaluate safety, and PK findings at a given dose level or to add cohorts to evaluate up to 2 additional dose levels. The study procedures for these additional participant(s)/cohort(s) will be the same as those described for other study participants/cohorts.

### **6.7. Intervention after the End of the Study**

Not applicable.

## 7. DISCONTINUATION OF STUDY INTERVENTION AND PARTICIPANT DISCONTINUATION/WITHDRAWAL

### 7.1. Discontinuation of Study Intervention

In rare instances, it may be necessary for a participant to permanently discontinue study intervention. If study intervention is permanently discontinued due to an adverse event, the participant will remain in the study to be evaluated for resolution of the event or return of labs to acceptable levels. See the SOA for data to be collected at the time of discontinuation of study intervention.

If a participant withdraws from the study, he/she must complete a follow-up visit.

#### 7.1.1. Gastrointestinal Events (diarrhea or colitis)

[figure not shown]
Grade	Diarrhea	Management	Follow-up
Mild (Grade 1)  An event that is easily tolerated by the participant, causing minimal discomfort and not interfering with everyday activities	Increase of <4 stools per day over Baseline	
 
Administer antidiarrheal and symptomatic treatment as appropriate
 
Discuss participant continuation in the trial with Sponsor/Medical Monitor
 
	
Symptoms resolve to baseline within 3 days:
 
 
Provide close follow-up to evaluate for increased severity.
 
 
Symptoms ongoing > 3 days:
 
 
Consider following algorithm for Grade 2 events
 

Moderate (Grade 2)  An event that causes sufficient discomfort and interferes with normal everyday activities	Increase of 4 - 6 stools per day over Baseline	
 
Interrupt study drug(s)
 
Administer antidiarrheal and symptomatic treatment
 
Investigate etiology; consider consulting GI service
 
Discuss participant continuation in the trial with Sponsor/Medical Monitor
 
	
Symptoms resolve to ≤ Grade 1 or baseline within 7 days:
 
 
Continue follow-up and evaluate for any increased severity.
 
 
Symptoms ongoing > 7 days, blood or mucus in stool, or ulceration/bleeding on endoscopy:

Grade	Diarrhea	Management	Follow-up
			
 
Consider following algorithm for Grade 3 events
 

Severe (Grade 3-4) An event that prevents normal everyday activities	Grade 3: Increase of $\geq 7$ stools per day over Baseline; incontinence; hospitalisation indicated  Grade 4: life-threatening consequences; urgent intervention indicated	
 
Discontinue study drug(s)
 
Consult GI service
 
Discuss participant continuation in the trial with Sponsor/Medical Monitor
 
	
Symptoms ongoing:
 
 
Continue follow up of participant
 
Discuss further management with GI consultant and Sponsor/Medical Monitor
 

### 7.1.2. Liver Chemistry Stopping Criteria

Study intervention will be discontinued for a participant if liver chemistry stopping criteria are met:

#### Phase I Liver Chemistry Stopping Criteria – Liver Stopping Event Algorithm

Abbreviations: ALT = alanine transaminase; INR = international normalized ratio; SAE = serious adverse event; ULN = upper limit of normal.

Liver Safety Required Actions and Follow up Assessments Section can be found in [Appendix 6](#).

**Liver chemistry stopping and increased monitoring criteria** have been designed to assure participant safety and evaluate liver event etiology.

Discontinuation of study intervention for abnormal liver tests is required when:

- a participant meets one of the conditions outlined in the algorithm
- OR
- when in the presence of abnormal liver chemistries not meeting protocol-specified stopping rules, the investigator believes study intervention discontinuation is in the best interest of the participant.

#### 7.1.2.1. Study Intervention Restart or Rechallenge after liver stopping criteria met

Study intervention restart or rechallenge after liver chemistry stopping criteria are met by any participant in this study is not allowed.

### 7.1.3. QTc Stopping Criteria

- The Fridericia QT correction formula (QTcF) *must* be used for *each individual participant* to determine eligibility for and discontinuation from the study. This formula may not be changed or substituted once the participant has been enrolled. Safety ECGs and other non-protocol specified ECGs are an exception.
- The QTc should be based on averaged QTc values of triplicate electrocardiograms obtained over a brief (e.g., 15 minute) recording period.
- A participant that meets either bulleted criterion below will be withdrawn from the study.
  - QTcF > 500msec,
  - Change from baseline: QTcF >60msec

See Section 1.3 for data to be collected at the time of study intervention discontinuation and follow-up and for any further evaluations that need to be completed.

### 7.1.4. Individual Stopping Criteria

- Any participant who experiences an SAE will be withdrawn from the study.
- Any participant who experiences an AE of moderate or severe intensity that is considered attributable to dosing with GSK3882347 will be withdrawn from the study.
- If a participant develops COVID-19 like symptoms during the course of the study the following actions should be taken:
  - During Part 1 (SAD portion of the study), participants who develop a high clinical index of suspicion for COVID-19 disease should be isolated and tested for COVID-19 in accordance with site procedures.
  - During Part 2 (MAD portion of the study), study treatment should be halted for any participants who develop a high clinical index of suspicion for COVID-19 disease; they should be isolated and tested for COVID-19 in accordance with site procedures.
  - In both cases, assessments should be continued as per the protocol during this period; withdrawal of participants from the study will be at the discretion of the Principal Investigator, but should first be discussed and agreed with the GSK Medical Monitor.

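### Section 7.1 keeps a participant stopped for an adverse event in the study while 7.1.4 withdraws the same participant, and 7.1.1 and 7.1.4 conflict on drug-attributed moderate diarrhoea

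*Protocol*

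**What the plan says.** Section 7.1 of the protocol addresses permanent discontinuation of study intervention because of an adverse event: "the participant will remain in the study to be evaluated for resolution of the event". It sends the reader to the schedule of activities ("See the SOA for data to be collected at the time of discontinuation of study intervention") and adds "If a participant withdraws from the study, he/she must complete a follow-up visit".

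Section 7.1.4, a subsection of 7.1, states "Any participant who experiences an SAE will be withdrawn from the study" and "Any participant who experiences an AE of moderate or severe intensity that is considered attributable to dosing with GSK3882347 will be withdrawn from the study". Section 7.1.3 has a parallel rule for QTcF: "A participant that meets either bulleted criterion below will be withdrawn from the study". It closes with "See Section 1.3 for data to be collected at the time of study intervention discontinuation and follow-up".

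Section 7.3 describes leaving the study as permanent discontinuation of both intervention and study at that point. An early discontinuation visit, using the follow-up visit's assessments, is to be done if possible.

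For diarrhoea, the Grade 2 (moderate) row of 7.1.1 has the site interrupt study drug, treat, look for a cause, and discuss with the sponsor or Medical Monitor whether the participant continues in the trial. The risk table in 2.3.2 also has dosing interrupted for Grade 2, and says that no restart is planned only for Grade 3-4.

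**The concern.** A site applying these rules to one participant gets two answers. Under 7.1 the participant stays in the study; under 7.1.4 the participant leaves it. For moderate diarrhoea judged attributable to the drug, 7.1.1 leaves continuation open and 7.1.4 closes it.

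Safety is a primary objective of this first-in-human study, and gastrointestinal toxicity is the only investigational-product risk listed in 2.3.2. Which text is followed bears on three things:

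- whether the remaining routine safety assessments are carried out;
- whether the participant is counted in the summary of AEs leading to withdrawal (section 9.4.1), if that summary counts leaving the study;
- whether the participant has discontinued the study and so becomes eligible for replacement (synopsis, Number of Participants).

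**Working it through.** The plan gives no figure to reproduce here. The check compares the texts and then bounds the effect.

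**1. Remain or leave.**

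| Event | Section 7.1 | Section 7.1.4 |
|---|---|---|
| SAE that permanently ends dosing | stays in study for evaluation | leaves study, whatever the causality |
| Attributed moderate or severe AE that permanently ends dosing | stays in study for evaluation | leaves study |

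No sentence says which prevails.

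**2. Could withdrawal in 7.1.4 simply mean no more dosing?** The closing line of 7.1.3 refers to discontinuation of intervention, so this may have been intended. But the COVID-19 bullets in 7.1.4 separate the two ideas. In Part 2 treatment is halted while "assessments should be continued as per the protocol during this period", and withdrawal from the study is a further decision for the Principal Investigator, agreed first with the Medical Monitor. The wording therefore does not settle the meaning.

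**3. QTc.** The conflict with 7.1 arises under 7.1.3 only when the QTcF finding is also an AE, that is, when the investigator judges it clinically significant (Appendix 3, 10.3.1).

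**4. Schedule of activities.** Sections 7.1 and 7.1.3 both cite it for data to collect when intervention stops. Leaving the study is covered through 7.3 and the follow-up visit. Tables 1 to 4 contain no entry for stopping intervention alone.

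**5. Diarrhoea.** The Grade 2 definition in 7.1.1 and the moderate intensity definition in 10.3.3 are identical. An attributed Grade 2 event is therefore always a moderate attributable AE under 7.1.4. Section 7.1.1 makes no exception for attributed events. The Grade 3-4 row also leaves continuation in the trial to discussion after the drug is discontinued, so the conflict extends to attributed severe events. Grade 2 events that are neither attributed nor serious raise no conflict.

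**6. Size: laboratory draws in Part 1.** Table 2 reads as post-dose safety draws at 24, 48, 72 and 96 h, which is 4. The table is broken in extraction, so the columns should be checked against the original.

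- AE before 24 h: 0 to 4 of 4 draws not taken.
- AE between 24 and 48 h: 0 to 3 not taken.
- The lower end applies if participants stay in the unit until scheduled assessments are complete (synopsis and 4.1). The upper end applies if 7.1.4, read with 7.3, takes effect at once.
- Laboratory sets left in the worst case: 1 (the mandatory follow-up visit), or 2 if the early discontinuation visit is held separately.

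**7. Size: withdrawal proportion for one participant.** Part 1 dose level: 0/6 or 1/6 = 16.7%. Part 2 cohort: 0/8 or 1/8 = 12.5%.

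**8. Escalation minimum (9.5.1: four active in Part 1, five in Part 2).** Part 1: 6 − 1 = 5 and 6 − 2 = 4 still suffice; 6 − 3 = 3 does not. Part 2: 8 − 1 = 7 and 8 − 3 = 5 suffice; 8 − 4 = 4 does not. One departure does not affect escalation.

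**The case against.** Section 7.3 opens with withdrawal at the participant's request or the investigator's discretion and never mentions the mandatory criteria, so applying its immediate effect to 7.1.4 is an inference. Section 7.1.4 could also be read as the specific rule under the general one in 7.1. Follow-up is largely kept either way: clinically significant laboratory values are repeated until they settle (8.2.5), related and serious AEs remain the investigator's responsibility (8.3), and SAEs are followed to resolution or stabilisation (8.3.3).

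On diarrhoea, the instruction to discuss continuation appears in every grade row, including Grade 1, and so may be routine consultation. A site could interrupt, discuss, attribute and then withdraw without breaching either section. Within a Part 1 period only one dose is given, so interruption within a period matters only in Part 2.

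On size, four missed draws is the extreme, the withdrawal table's definition is left to the analysis plan, replacement is discretionary, and the study stopping rules in 7.2 could halt dosing before several departures accumulate.

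These points limit the consequence and are accepted as limits. They do not remove the conflict. The sentence in 7.1 is about an AE that ends dosing, which is the main case 7.1.4 governs, so calling one general and the other specific does not rank them. The sequential reading of the diarrhoea rules works only if the discussion in 7.1.1 cannot end in continuation for an attributed event, and 7.1.1 does not say that. By ruling out restart for Grade 3-4 only, 2.3.2 leaves it open for Grade 2.

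**Conclusion.** The concern holds. The protocol states conflicting rules on whether participants with SAEs, or with attributed moderate or severe AEs that end dosing, remain in the study. It also states conflicting rules on attributed Grade 2 diarrhoea. This should be corrected, although the effect on the data is modest. The triggering event is recorded and a follow-up visit is required on either reading. What is at risk is mainly routine post-event assessments and disposition coding. The laboratory range assumes the reading of Table 2 given above, and the 16.7% and 12.5% figures assume that the AE-withdrawal summary counts study withdrawal. How many participants would be affected cannot be known from the protocol.

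**What to change.** Reconcile sections 2.3.2, 7.1, 7.1.1, 7.1.3, 7.1.4 and 7.3 so that stopping study intervention and leaving the study are separate, consistently used terms. In the schedule of activities, which 7.1 and 7.1.3 already cite, state which of the scheduled safety assessments continue after dosing stops. Give attributed moderate gastrointestinal events one handling across 2.3.2, 7.1.1 and 7.1.4, and check the Grade 3-4 row at the same time. Which clinical rule applies is for the sponsor and investigator to decide.

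The cost is protocol wording and a schedule note. Any continued assessments are already scheduled and should concern only a few participants.
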